6.1.2.3. Use of Antipyretic Medications Within 7 Days After Vaccination

- Analysis set: Safety. Refer to [Section 4](#) for visit-specific populations.
- Analysis methodology: Descriptive summary statistics and Clopper-Pearson CIs.
- Intercurrent events and missing data: Participants will be analyzed according to the vaccine they actually received. Missing e-diary data will not be imputed.
- For each group, n, %, and 95% CI will be presented by vaccine group for the following variables:
 - Use of antipyretic medication on any day (Days 1-7) after vaccination.

6.1.2.4. Serious Adverse Events, Medically Attended Adverse Events, and Newly Diagnosed Chronic Medical Conditions

- Analysis set: Safety. Refer to [Section 4](#) for visit-specific populations.
- Analysis methodology: Descriptive summary statistics and Clopper-Pearson CIs.
- Intercurrent events and missing data: Participants will be analyzed according to the vaccine they actually received. Missing AE dates will be handled according to the Pfizer safety rules.
- For each group, the numbers and percentage of participants with MAEs, SAEs, and NDCMCs for each of the analysis intervals defined in [Table 4](#) will be summarized. For the events during the vaccination and follow-up phase, the (n), %, and 95% CI may be presented for any event, for each SOC, and for each PT within each SOC.

6.1.2.5. Adverse Events

- Analysis set: Safety. Refer to [Section 4](#) for visit-specific populations.
- Analysis methodology: Descriptive summary statistics and Clopper-Pearson CIs. The Miettinen and Nurminen procedure to calculate the 95% CI of the difference in percentages for Tier 1 and Tier 2 events.
- Intercurrent events and missing data: Participants will be analyzed according to the vaccine they actually received. Missing AE dates will be handled according to the Pfizer safety rules.
- For each group, the numbers of participants with AEs for the first 4 analysis intervals defined in [Table 4](#) will be summarized. The (n), %, and 95% CI may be presented for any event, for each SOC, and for each PT within each SOC.

For both Tier 1 and Tier 2 events (AEs by PTs during the vaccination period), the 95% CIs for the difference in the percentage of participants reporting the events between the MenABCWY and Trumenba combined groups will be calculated using the Miettinen and Nurminen method. Descriptive summary statistics (counts and percentages and associated Clopper-Pearson 95% CIs) will be provided for all events. There is no Tier 1 event identified for MenABCWY at this stage. The difference in the percentage of participants reporting the events between the MenABCWY and Trumenba combined groups for the analysis intervals will also be presented.

- Nonserious AEs are not required to be reported during the follow-up phase; however, if nonserious AEs during the follow-up phase are recorded in the database (excluding MAEs and nonserious NDCMCs), these data may be listed separately.

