- Ask the parent(s)/legal guardian or participant to report the maximum diameter of the redness and/or swelling at the injection site to the investigator daily until the reaction becomes ≤ 21 caliper units.
- Provide the parent(s)/legal guardian or participant with a contact card ([Section 10.1.10](#)).
- Ask the parent(s)/legal guardian or the participant to contact the investigator immediately if any significant illness or hospitalization occurs.
- Schedule an appointment for the next study visit and confirm that it is scheduled within the time window per protocol.
- Remind the parent(s)/legal guardian or participant to bring the e-diary to the next study visit.
- Complete the source documents.
- Complete the CRF and update the investigational product accountability records.

Between visits, review the e-diary data online at frequent intervals. Contact the parent(s)/legal guardian or the participant to obtain stop dates for any local reactions, systemic events, or use of antipyretic medication that were ongoing on the last day that the e-diary was completed. The stop dates should be documented in the source documents and the information entered into the CRF at the next study visit of the participant.

8.10.2.2. Visit 2 (28 to 42 Days After Visit 1), Post–Vaccination 1 Telephone Contact

- Visit 2 will be a telephone contact for participant in the safety subset (Groups 5-8).
- Ensure that the participant continues to be eligible for the study, and continues to comply with contraception requirements detailed in [Section 5](#).
- Ensure that the participant continues to meet none of the withdrawal criteria and none of the temporary delay of blood draw criteria as described in [Section 5.2.1](#).
- Review the participant's e-diary data since the previous visit and follow up on any ongoing reactogenicity or use of antipyretic medication.
- Complete the Study Visit/Telephone Contact AE Checklist to:
 - Inquire whether the participant had any NDCMCs since the last visit. Inquire whether the participant had any of the following related to an AE since the last visit: hospitalizations, visits to other medical facilities, medication use, or missed days of school or work. Please refer to the SRM for additional details.
 - Inquire about neuroinflammatory and autoimmune conditions, such as transverse myelitis, uveitis, optic neuritis, and multiple sclerosis. Please refer to the SRM for additional details.

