2.2. Study Design

This is a Phase 3, randomized, active-controlled, observer-blinded multicenter trial in which approximately 2413 participants ≥ 10 to <26 years of age will be randomly assigned to receive either MenABCWY and saline, or Trumenba and MenACWY-CRM. The study will include evaluation of both ACWY-naïve and ACWY-experienced individuals. All participants will be naïve to any meningococcal group B vaccine prior to enrollment. ACWY-experienced is defined as receiving a US-licensed MenACWY vaccine at least 4 years prior to enrollment. [Table 2](#) illustrates the study design.

Participants in Groups 1 through 4 will be considered an immunogenicity subset and will contribute to both the safety and immunogenicity analyses; these participants will have blood drawn prior to Vaccination 1 and 1 month after Vaccinations 1 and 2. Participants in Groups 5 through 8 will be considered a safety subset and will contribute to the safety analysis only, and will not have blood drawn for immunogenicity evaluations.

Randomization will be stratified by prior vaccination history. Overall, approximately 1225 ACWY-naïve and 1188 ACWY-experienced participants (having received 1 dose of Menactra or Menveo ≥ 4 years prior to the date of randomization) will be enrolled. Of these total participants, up to 675 ACWY-naïve and 1013 ACWY-experienced participants will contribute to the immunogenicity subset.

Participants enrolled in the immunogenicity subset will contribute to both the immunogenicity and safety evaluations. Additionally, participants will be enrolled in a safety subset that will contribute exclusively to the safety evaluation. Numbers enrolled in the safety subset will therefore be based on numbers needed to achieve an overall number of enrolled participants, all of whom will contribute to the safety evaluation. The numbers to be enrolled by group across immunogenicity and safety subsets as stated in the protocol (Protocol amendment 1, Section 1.2 and Table 1) are estimates only.

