3.5.1.1. Analysis Intervals

There will be 6 analysis intervals for the AE data collected via the CRF (Table 5). The analysis populations used for these intervals are described in detail in [Section 4](#).

Table 5. Analysis Intervals for AEs, SAEs, MAEs, NDCMCs, and Days Missing School or Work Because of AEs

#	Analysis Interval	Analysis Population	Interval Start Date (Inclusive)	Interval Stop Date (Inclusive)	Safety Data
1	Within 30 days after Vaccination 1	Vaccination 1 safety	Vax 1 date	Vax 1 date + 30 days	AEs, SAEs, MAEs, NDCMCs
2	Within 30 days after Vaccination 2	Vaccination 2 safety	Vax 2 date	Vax 2 date + 30 days	AEs, SAEs, MAEs, NDCMCs
3	Within 30 days after any vaccination	Safety	Vax 1 date or Vax 2 date	Vax 1 date + 30 days or Vax 2 date + 30 days	AEs, SAEs, MAEs, NDCMCs
4	During vaccination phase	Safety	Visit 1 date	Visit 4 date (or end of vaccination day)	AEs, SAEs, MAEs, NDCMCs, days missing school or work because of AEs
5	During follow-up phase	Follow-up safety	Visit 4 date + 1, or end of vaccination date + 1 for early-withdrawal participants	Visit 5 date	SAEs, MAEs, NDCMCs
6	Throughout study	Safety	Visit 1 date	Visit 5 date	SAEs, MAEs, NDCMCs

Abbreviations: MAE = medically attended adverse event; NDCMC = newly diagnosed chronic medical condition.

Two analysis intervals will be applied to immediate AEs (Table 6).

Table 6. Analysis Intervals for Immediate AEs

#	Analysis Interval	Analysis Population	Interval Start Date/Time (Inclusive)	Interval Stop Date/Time (Inclusive)
1	Vaccination 1	Vaccination 1 safety	Vax 1 time	Vax 1 time + 30 minutes
2	Vaccination 2	Vaccination 2 safety	Vax 2 time	Vax 2 time + 30 minutes

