4.1. Vaccine/Stratum Misallocation

- Randomized into the wrong MenACWY stratum: These participants will be included in the safety population for the safety analysis and will be reported under the MenACWY stratum according to true MenACWY history. These participants will also be included in the mITT population for immunogenicity analyses if data are available, and will be reported under the MenACWY stratum according to their true MenACWY history (MenACWY experience recorded on the CRF for prior MenACWY history). However, these participants will be excluded from the analyses using evaluable immunogenicity population(s) for the MenACWY endpoints, but included in the analyses using evaluable immunogenicity population(s) for the MenB endpoints. A participant's true MenACWY history (naïve/experienced) will be ascertained programmatically from the prior meningococcal vaccine data set in the clinical database before the planned unblinding. Serogroups contained within the prior meningococcal vaccine received will be determined by the sponsor's global medical monitor.
- Participants randomized to the safety subset but for whom immunogenicity data are collected according to the CRF: These participants will be reported according to their true immunogenicity subset per the CRF. A participant's true immunogenicity/safety assignment will be ascertained programmatically in the clinical database before the planned unblinding. These participants will be included in the safety population and the mITT population. For the evaluable populations, they will be excluded.

- Vaccinated but not randomized: These participants will be included in the safety population for safety analysis and will be reported under the vaccine group based on the vaccine received, but will be excluded from immunogenicity analyses.
- Randomized but not vaccinated: These participants will be included in the ITT population and excluded from any safety analyses. They may be included in the mITT population if any assay results are available and will be reported under their randomized group for immunogenicity analyses.
- Randomized but received incorrect vaccine: These participants will be included in the mITT population for immunogenicity analyses if data are available and will be reported under the vaccine group based on the randomized vaccine. These participants will also be included in the safety population for safety analysis and will be reported under the vaccine group based on the vaccine received.

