5.2.1.2. Safety Data

All safety endpoints (including reactogenicity data recorded from the e-diary and AE data recorded from the CRF) will be summarized with percentages and 95% exact CIs (Clopper-Pearson method) for each group.

For both Tier 1 and Tier 2 events (AEs by PTs during the vaccination period), the 95% CIs for the difference in percentage of participants reporting the events between MenABCWY and Trumenba combined groups will be calculated using the Miettinen and Nurminen method.

The CIs presented for the safety data will not be used to test hypotheses but will be used to determine which events may need further clinical investigation. No adjustment for multiplicity is needed. There are no Tier 1 events identified for MenABCWY.

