6.1.2. Primary Safety Endpoints

Safety endpoints will be summarized by MenABCWY groups (Groups 1, 3, 5, and 7 combined) and Trumenba groups (Groups 2, 4, 6, and 8 combined). The reactogenicity data may also be summarized by true MenACWY history (naïve/experienced).

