6.4. Subset Analyses

Subgroup analyses may be performed on the primary and secondary immunogenicity and safety endpoints described in [Section 6.1.1](#), [Section 6.1.2](#), and [Section 6.2](#). No subgroup analysis is planned for rare events (endpoints with less than 1% of participants in any group). Subgroups can include age strata (10 to <18 years; 18 to <26 years), sex, race, and ethnicity.

If a subgroup variable (eg, race) does not have more than 1 group with greater than 5% participants in the group, the corresponding subset analyses may not be reported.

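### The pooled adverse-event differences are unstratified although the vaccine ratio runs from 2:1 to 10:1 across groups, so they can be confounded by ACWY history and by subset

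*SAP*

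**What the plan says.** SAP 6.1.2 sets the pooling: "Safety endpoints will be summarized by MenABCWY groups (Groups 1, 3, 5, and 7 combined) and Trumenba groups". The Trumenba side consists of the even-numbered groups. SAP 5.2.1.2 and 6.1.2.5 then compare these two pooled arms. The rule for the first two tiers reads: "the 95% CIs for the difference in the percentage of participants reporting the events between the MenABCWY and Trumenba combined groups will be calculated". The method named is Miettinen-Nurminen (M-N). Section 6.1.2.5 adds group differences for the analysis intervals, with no interval method named. Protocol 9.4.2 describes the same combined-group method. No stratification or adjustment is mentioned in either document.

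The Tier 2 intervals cover the vaccination period. SAP Table 5 (interval "During vaccination phase") runs this from Visit 1 through the Visit 4 date. On their use, SAP 5.2.1.2 says the safety intervals "will not be used to test hypotheses but will be used to determine which events may need further clinical investigation".

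On design, SAP 2.2 states: "Randomization will be stratified by prior vaccination history"; region is a further stratification factor. Groups 5-8 have telephone contacts at Visits 2 and 4 and no blood draws (Protocol 1.2 and 8.10.2). For subgroups, SAP 6.4 says: "Subgroups can include age strata (10 to <18 years; 18 to <26 years), sex, race, and ethnicity". The optional display by ACWY history in SAP 6.1.2 covers reactogenicity only.

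**The concern.** Randomization protects the vaccine comparison within each ACWY-by-subset cell. Pooling cells with different allocation ratios gives that protection up. Any factor that differs between cells and affects AE rates or AE reporting then becomes a confounder, and a larger sample does not remove it.

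Subset is the more plausible of the two factors. Protocol 2.3 lists faintness, dizziness, fainting, pain, swelling, bruising and infection as blood-sampling risks, and only Groups 1-4 have blood drawn. Reporting may also be lower by telephone than in person. Either mechanism lowers the percentage in the arm with more safety-subset participants, which is MenABCWY, so the investigational vaccine would look safer than it is. A rate difference by ACWY history could add to this or offset it.

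The safety objective is descriptive, but the intervals serve as a screen. A biased screen can flag a term with no vaccine effect or miss one that has an effect.

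**Working it through.** **Inputs.** Planned group sizes come from Protocol 1.2 and SAP Table 2. They reproduce the totals in Protocol 9.2.2: 450 + 675 + 500 + 125 = 1750 on MenABCWY and 225 + 338 + 50 + 50 = 663 on Trumenba + MenACWY-CRM, 2413 in all.

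| Cell | MenABCWY | Trumenba | Ratio | Share of 1750 | Share of 663 | Difference (points) |
|---|---|---|---|---|---|---|
| Naive, immunogenicity (1 v 2) | 450 | 225 | 2.0 | 25.7% | 33.9% | -8.2 |
| Experienced, immunogenicity (3 v 4) | 675 | 338 | 2.0 | 38.6% | 51.0% | -12.4 |
| Naive, safety (5 v 6) | 500 | 50 | 10.0 | 28.6% | 7.5% | +21.0 |
| Experienced, safety (7 v 8) | 125 | 50 | 2.5 | 7.1% | 7.5% | -0.4 |

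**Imbalance.**
- ACWY-naive: 950/1750 = 54.3% vs 275/663 = 41.5%, a gap of 12.8 points.
- Safety subset: 625/1750 = 35.7% vs 100/663 = 15.1%, a gap of 20.6 points.
- Naive share within Groups 1-4: 450/1125 = 40.0% vs 225/563 = 40.0%. Within Groups 5-8: 500/625 = 80% vs 50/100 = 50%. The ACWY imbalance therefore comes wholly from the safety subset.

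**Bias with no vaccine effect.** The expected crude difference is the sum over cells of (share difference × cell rate). With additive effects:

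bias = 0.128 × (naive − experienced rate) + 0.206 × (safety − immunogenicity subset rate).

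**Preferred terms (all rates assumed).**
- 25% lower reporting in Groups 5-8: 0.206 × 0.25 × 1% = 0.05 points, and × 5% = 0.26 points. The bias is -0.05 to -0.26 points.
- 50% lower reporting: -0.10 to -0.52 points.
- Term caused only by blood sampling, at 2% or 3% in Groups 1-4: 0.206 × 2 = 0.41 and 0.206 × 3 = 0.62, so -0.41 or -0.62 points.

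**How often the 95% M-N interval contains zero with no vaccine effect** (40,000 simulated trials per scenario; simulation error at 87% is √(0.87 × 0.13/40,000) = 0.17 points):

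| Scenario | Crude | Stratified |
|---|---|---|
| 5% term, 25% lower in Groups 5-8 | 93.8% | about 95% |
| 5% term, 50% lower in Groups 5-8 | 90.7% | 95.1% |
| Blood sampling only, 2% | 87% | 95% |
| Blood sampling only, 3% | 83% | 95% |

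**Masking.** Take a true 1.5-fold MenABCWY excess on a term at 5% in Groups 1-4 and 2.5% in Groups 5-8. The crude interval excludes zero in 29% of trials and the stratified interval in 54%.

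**Any AE, assumed 40% rate** (Phase 2 rates were 39.2% and 40.7%, Protocol 2.2.2.3). A 5-point lower rate in the safety subset gives -1.0 points, and a 10-point lower rate gives -2.1. Adding a 10-point higher rate in naive participants to the latter gives 1.28 − 2.06 = -0.8. The crude standard error is √(0.4 × 0.6 × (1/1750 + 1/663)) = 2.23 points.

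**Cost of stratifying.** Mantel-Haenszel weights n₁n₀/(n₁+n₀) are 150.0, 225.2, 45.5 and 35.7 (32.9%, 49.3%, 10.0% and 7.8%), summing to 456.4. The crude equivalent is 1750 × 663/2413 = 480.8. At equal rates the standard error grows by √(480.8/456.4) = 1.026.

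**The case against.** Nothing in the documents shows that the cell rates differ. Phase 2 AEs were described as similar by ACWY history among MenABCWY recipients, and no rates by subset are given. Every group uses the same AE checklist, attends Visits 1 and 3 in person and has Visit 5 by telephone. This stands: the bias is possible, not demonstrated. The Phase 2 summary does not, however, address subset, which carries the larger weight.

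Many Tier 2 terms will be rare. The rule of four participants in one arm corresponds to 4/1750 = 0.23% or 4/663 = 0.60%. For terms at 0.25-0.5% with 25-50% lower reporting in Groups 5-8, simulated crude coverage is 94.8-95.4%. This also stands: the problem concerns the commoner terms.

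Three of the four AE intervals end 30 days after vaccination, while the Visit 2 and Visit 4 draws fall at days 28-42. The blood-draw mechanism therefore acts mainly in the vaccination phase. That is correct, but the vaccination phase is where the Tier 2 intervals are computed.

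Some planned analyses might help. Related AEs are summarized separately (SAP 6.6.1.1), and the subgroup list in SAP 6.4 is open-ended. Neither plans an adjusted group difference, and the subgroup wording commits to nothing.

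The analysis is exploratory, and flagged terms go to clinical review. Review can discount a false flag, but it cannot recover a term that was never flagged.

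Group sizes are stated to be estimates, and slots may move from the safety to the immunogenicity subset. The realized imbalance may be smaller; stratification adapts to whatever mix occurs.

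**Conclusion.** The concern holds. The unequal ratios are planned, the AE differences are taken on pooled arms with no stratification named, and no planned AE analysis removes the imbalance. The bias weights, 0.21 for subset and 0.13 for ACWY history, follow exactly from the planned sizes. What they multiply is unknown. With equal cell rates the bias is zero, and with modest reporting gaps or rare terms it is negligible. It becomes material for commoner terms with about half the reporting in Groups 5-8, or for terms driven by blood sampling, where false exclusions of zero mostly favor MenABCWY. The primary immunogenicity conclusions are not affected. Confidence is moderate because every cell rate used here is assumed. The change is justified because it is cheap and removes a bias that the design itself creates.

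**What to change.** In SAP 5.2.1.2 and 6.1.2.5, compute the unsolicited-AE differences (the Tier 1/Tier 2 intervals and the by-interval differences) with a stratified M-N method. Use Mantel-Haenszel weights over the four cells of ACWY history by subset (Groups 1-4 vs 5-8). SAP 4.1 already derives true ACWY history, and for subset it says of participants randomized to the safety subset who have immunogenicity data: "These participants will be reported according to their true immunogenicity subset per the CRF". Keep the crude percentages and Clopper-Pearson intervals for each arm. Reactogenicity needs no change, since no group differences are planned for it.

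A simpler alternative is to repeat the Tier 2 table in Groups 1-4 only, where both factors are balanced by design.

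**Cost.**
- No new data; SAP wording and a stratified M-N routine. Protocol 9.4.2 describes the combined-group method, so the sponsor should check whether it needs matching text.
- In simulation, intervals are about 3% wider, or about 6% for a term absent from Groups 5-8.
- Groups 5-8 receive 17.8% of the weight although they supply 35.7% of MenABCWY recipients, and the stratified difference will not equal the subtraction of the displayed percentages. A table footnote should say so.
- Groups 6 and 8 have 50 participants each, so strata are sparse for rare terms. At a 1% rate the stratified interval could still be computed in every simulated data set, with coverage 95.5%.

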6.1.2.6. Immediate Adverse Events

- Analysis set: Safety. Refer to [Section 4](#) for visit-specific populations.
- Analysis methodology: Descriptive summary statistics and Clopper-Pearson CIs.
- Intercurrent events and missing data: Participants will be analyzed according to the vaccine they actually received. Missing AE dates will be handled according to the Pfizer safety rules.
- The number and percentage of participants reporting AEs occurring within the 30-minute observation period immediately after vaccination will be summarized according to the first 2 analysis intervals defined in [Table 6](#). These summaries will include 95% Clopper-Pearson CIs.

6.1.2.7. Days Missing School or Work

- Analysis set: Safety. Refer to [Section 4](#) for visit-specific populations.
- Analysis methodology: Descriptive summary statistics and Clopper-Pearson CIs.
- Intercurrent events and missing data: Participants will be analyzed according to the vaccine they actually received. Missing AE dates will be handled according to the Pfizer safety rules.
- The total number of days a participant missed school and/or work will be descriptively summarized.

6.2. Secondary Endpoints

6.2.1. Secondary Immunogenicity Endpoints

Hypothesis testing for the first secondary objective will be performed only if the primary objectives are successfully achieved.

6.2.1.1. hSBA Titer for Each of the MenACWY Test Strains for ACWY-Naïve Participants

